## 5 STATISTICS

### 5.1 DETERMINATION OF SAMPLE SIZE

In the Plethora study, “Development of the Premature Ejaculation Bothersome Evaluation Questionnaire (PEBEQ): Quantitative Research Stage, 10/56 = 18% of subjects had improvements of 1 unit or more on Item 3 (event-specific bother). This data was collected in the development and testing of the PEBEQ itself. No treatments were involved, so this can be considered to be a control success rate. Treatment change in “distress” scores of the IPE measured throughout the Sponsor study PSD502-PE-002, a double-blind placebo study, appear to support the anticipation of a 30% treatment change in the “bother” score of the PEBEQ in the current pilot study. Although there is no established criterion for a clinically meaningful success rate, it is hoped that treatment will result in more than doubling the success rate in the present study.

Randomizing 100 subjects (50 per treatment arm) is feasible for this pilot study in order to assess the proportion of subjects who achieve a 1-point or greater improvement over 4 weeks in the mean PEBEQ Item 3 (event-specific bother). This sample size is sufficient to detect a difference of 30% in success rates when the placebo rate is 20%, with power 80% using a chi square test with a 5% Type I error rate. It allows for a 10 percent dropout rate.

In order to assess the psychometric properties of the PEBEQ Item 3 (event-specific bother), the 100 subjects will be used. This sample size is sufficient to provide estimates of meaningful change; in a validation study conducted on 56 males to test the psychometric performance of the full PEBEQ including the General and Event Specific subscales, the standard error associated with correlations of about 0.50 on a number of PROs was about 0.12. With a sample size of 100, the standard error is expected to decrease to around 0.05 to 0.08.

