The placebo spray will be administered in the same manner as the PSD502 spray.

Criteria for Evaluation:

Efficacy:

The primary efficacy variable is the:

- Success on the PEBEQ Item 3 (event-specific bother), where success is defined as having a 1-point or greater improvement between the mean response over the treatment period and the mean response during the baseline period

The secondary efficacy variables are the:

- PGI-C
- PGI-S
- PGI-C-Bother
- IELT
- IEQI
- Change from baseline in the IPE Control, Distress and Satisfaction Domain Scores
- Independent NRS Bother Item

The exploratory efficacy variables are the:

- PEBEQ Multi-Item Event Specific Subscale Total

- PEBEQ Multi-Item General Subscale Total

Psychometric:

- PEBEQ Item 3 (event-specific bother)

Safety:

Safety variables include study drug exposure, the nature, incidence, relationship and severity of AEs and serious AEs (SAEs), incidence of and reasons for withdrawals, laboratory parameters, use of concomitant medications, vital signs, findings on physical examination, 12-lead ECG and visual examination of the penis.

Statistical Methods

Sample Size: In order to assess the proportion of subjects who achieve a 1-point or greater improvement over 4 weeks in the mean PEBEQ Item 3 (event-specific bother), 100 subjects will be randomized into this pilot study, 50 per arm (allowing for a 10% dropout rate). This sample size is sufficient to detect a difference of 30% in success rates when the placebo rate is 20%, with power 80% using a chi square test with a 5% Type I error rate.

In order to assess the psychometric properties of the PEBEQ Item 3 (event-specific bother), the 100 subjects will be used. This sample size is sufficient to provide estimates of meaningful change; in a validation study conducted on 56 males to test the psychometric performance of the full PEBEQ including the General and Event Specific subscales, the standard error associated with correlations of about 0.50 on a number of patient reported outcomes (PROs) was about 0.12. With a sample size of 100, the standard error is expected to decrease to around 0.05 to 0.08.

Randomization:

A randomization schedule assigning subjects to treatment will be defined for each site and stratified by circumcision status. Each schedule will be blocked, independently of the other schedules.

Analysis Populations:

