A linear mixed effects model will be used to evaluate treatment effect on the two PEBEQ multi-item subscales during the study. The fixed effects are period (baseline or treatment period), treatment, period-by-treatment interaction and circumcision status and the random effects are site and subject within site.

Descriptive statistics will include sample size, number of missing observations, counts or mean values and standard deviations for discrete and continuous variables, respectively. Descriptive statistics will be provided for subgroup categories (treatment, site, circumcision status).

Psychometric Analysis:

The evaluation of test-retest reliability will be made using the intra-class correlation coefficient (ICC) using a two-way mixed effect model with absolute agreement for single measures. These analyses will be conducted using one pair of successive valid diary entries per subject where subject indicated no change from the PGI-S on the second sexual encounter. The primary analysis will use diary entries for sexual encounter 1 and sexual encounter 2. If the subject indicates having a change between sexual encounter 1 and sexual encounter 2, then that subject's diary entries for sexual encounter 2 and sexual encounter 3 will be used for the analysis; or if there is a change between 2 and 3, then diary entries for sexual encounter 3 and sexual encounter 4 will be used.

Convergent validity (demonstrating that different measures of the same concept substantially correlate when assessed concurrently) will be evaluated by examining

magnitude of correlations between the PEBEQ Item 3 (event-specific bother) and the Independent NRS bother item. Convergent validity would be supported when the PEBEQ Item 3 (event-specific bother) is substantially correlated (≥ 0.40).

Known-groups validity (the extent to which scores from a measure can discriminate between groups of participants that differ on a known relevant dimension, such as a measure/assessment of disease severity) will be examined using an analysis of variance (ANOVA) model to ensure adequate variability in the bother grouping variables based on (1) IEQI, (2) PGI-S and (3) groups defined by the IELT ≤ 30 seconds, >30 seconds- ≤ 1 minute, >1 minute- ≤ 2 minutes, and >2 minutes).

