#### **5.2.3.9 Psychometric Analyses**

##### Primary objective

The evaluation of test-retest reliability will be made using the intra-class correlation coefficient (ICC) using a two-way mixed effect model with absolute agreement for single

measures. These analyses will be conducted using one pair of successive valid diary entries per subject where subject indicated no change from the PGI-S on the second sexual encounter. The primary analysis will use diary entries for sexual encounter 1 and sexual encounter 2. If the subject indicates having a change between sexual encounter 1 and sexual encounter 2, then that subject's diary entries for sexual encounter 2 and sexual encounter 3 will be used for the analysis; or if there is a change between 2 and 3, then diary entries for sexual encounter 3 and sexual encounter 4 will be used.

Convergent validity (demonstrating that different measures of the same concept substantially correlate when assessed concurrently) will be evaluated by examining magnitude of correlations between the PEBEQ Item 3 (event-specific bother) and the Independent NRS bother item. Convergent validity would be supported when the PEBEQ Item 3 (event-specific bother) are substantially correlated ( $\geq 0.40$ ).

Known-groups validity (the extent to which scores from a measure can discriminate between groups of participants that differ on a known relevant dimension, such as a measure/assessment of disease severity will be examined using an analysis of variance (ANOVA) model to ensure adequate variability in the bother grouping variables based on (1) IEQI, (2) PGI-S and (3) groups defined by the IELT  $\leq 30$  seconds,  $>30$  seconds- $\leq 1$  minute,  $>1$  minute- $\leq 2$  minutes, and  $>2$  minutes).

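### The expected standard error of 0.05 to 0.08 at n = 100 does not follow from 0.12 at n = 56, which scales to about 0.09; 0.05 is out of reach at a correlation near 0.50

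*SAP*

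**What the plan says.** SAP section 5.1 gives the primary-endpoint sample size and then turns to the psychometric objective: "In order to assess the psychometric properties of the PEBEQ Item 3 (event-specific bother), the 100 subjects will be used". It calls this number sufficient and supports that with results obtained "in a validation study conducted on 56 males to test the psychometric performance of the full PEBEQ", where "the standard error associated with correlations of about 0.50 on a number of PROs was about 0.12". The projection follows: "With a sample size of 100, the standard error is expected to decrease to around 0.05 to 0.08".

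The Sample Size paragraph of the protocol synopsis makes the same argument. It reports that "the standard error associated with correlations of about 0.50 on a number of patient reported outcomes (PROs) was about 0.12" and gives the same range for 100 subjects.

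Neither document gives a formula, a different correlation for the new study, a different number of subjects behind the earlier correlations, or any gain from repeated encounters.

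One psychometric criterion is a threshold on a correlation. SAP section 5.2.3.9 says: "Convergent validity would be supported when the PEBEQ Item 3 (event-specific bother) are substantially correlated", with 0.40 as the cut-off. The Psychometric Analysis part of the protocol synopsis uses the same cut-off.

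**The concern.** Going from 56 to 100 subjects is less than a doubling, so a standard error should shrink by about a quarter. The plan has it shrink by a third (0.12 to 0.08) to more than a half (0.12 to 0.05).

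This is the only number offered for 100 subjects being enough for the psychometric work, which is a secondary objective. If it is too small, readers will expect tighter estimates than the study can give. Around a correlation of 0.50, a standard error of 0.05 puts the lower 95% limit at the 0.40 criterion, which suggests the study could separate the two values. At 0.09 it could not.

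**Working it through.** **Inputs.** All are from SAP section 5.1 and are repeated in the protocol synopsis: n = 56, correlation about 0.50, standard error about 0.12; planned n = 100; stated standard error at n = 100 of 0.05 to 0.08.

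**Step 1: reproduce the starting figure.** With r = 0.50 and n = 56, sqrt((1 − r²)/(n − 2)) = sqrt(0.75/54) = 0.118. This matches the stated 0.12, so the starting figure is plausible as it stands.

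**Step 2: scale to n = 100.** 0.12 × sqrt(56/100) = 0.12 × 0.748 = 0.0898. Using n − 1, n − 2 or n − 3 in place of n gives 0.0894, 0.0891 or 0.0887. If 0.12 is a rounded value, 0.115 gives 0.0861 and 0.125 gives 0.0935; the n − 3 factor takes the lowest of these to 0.0850. The formula of step 1 at n = 100 gives sqrt(0.75/98) = 0.0875.

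**Step 3: try other formulas at r = 0.50.**

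| Formula | n = 56 | n = 100 |
|---|---|---|
| sqrt((1 − r²)/(n − 2)) | 0.118 | 0.0875 |
| Large-sample, (1 − r²)/sqrt(n − 1) | 0.101 | 0.075 |
| Fisher z, back-transformed, (1 − r²)/sqrt(n − 3) | 0.103 | 0.076 |
| Simulated SD of r, bivariate normal | 0.103 | 0.076 |
| Spearman (Bonett-Wright), back-transformed | 0.109 | 0.081 |
| Zero correlation, 1/sqrt(n − 1) | 0.135 | 0.101 |
| Fisher z scale, 1/sqrt(n − 3) | 0.137 | 0.102 |
| Spearman, z scale | 0.146 | 0.108 |

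Only the first row reproduces 0.12 at n = 56, and it gives about 0.09 at n = 100. Some other rows come near 0.08 at n = 100, but they start from 0.10 to 0.11. None gives 0.05.

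**Step 4: what the stated range would need.**

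- Subjects, scaling from 0.12 at 56: 56 × (0.12/0.05)² = 323 for 0.05, and 56 × (0.12/0.08)² = 126 for 0.08. For 0.05, the first formula in the table needs 302 and the large-sample formula 226.
- Correlation giving 0.05 at n = 100: 0.87 by the first formula, 0.71 by the large-sample formula. At r = 0.60 the lowest value is still 0.064.
- Subjects behind the earlier correlations, if 0.12 is right: 100 × (0.05/0.12)² = 17 for 0.05, and 100 × (0.08/0.12)² = 44 for 0.08. The text says 56.

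**Step 5: consequence around r = 0.50 (normal approximation).**

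| Standard error | 95% half-width (1.96 × SE) | Lower 95% limit | Chance of observed r < 0.40 if true r = 0.50 |
|---|---|---|---|
| 0.05 | 0.098 | 0.402 | 2.3% |
| 0.08 | 0.157 | 0.343 | 10.6% |
| 0.0898 | 0.176 | 0.324 | 13.3% |

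**Sensitivity to dropout.** SAP section 5.1 says of the sample size: "It allows for a 10 percent dropout rate". With 90 evaluable subjects the scaled value is 0.12 × sqrt(56/90) = 0.095, further from the stated range.

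**The case against.** The strongest reply is that the upper end is about right and that 0.12 is the odd figure. The formula that reproduces 0.12 is the one used in the t test of zero correlation. The sampling standard deviation of a correlation of 0.50 is about 0.103 at n = 56 and 0.076 at n = 100. On that reading 0.08 is a fair statement of precision and 0.09 is slightly pessimistic. The Fisher z interval at n = 100 has a lower limit of 0.337, and the chance of observing less than 0.40 is about 10.8%; both are close to the 0.08 row above. This stands as a defense of 0.08 taken alone. It does not rescue the sentence, because no single formula tried gives both 0.12 at 56 and the stated range at 100, and it does nothing for 0.05.

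Second, the range may reflect a spread of correlations. At r = 0.70 the large-sample formula gives (1 − 0.49)/sqrt(99) = 0.051. That is possible, but the text speaks only of correlations of about 0.50 and gives no other value for this trial.

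Third, under SAP section 5.2.3.3 reliability and validity are assessed in everyone eligible who enters baseline, which may be more than 100. The stated standard error is nevertheless tied to a sample size of 100. The responsiveness and meaningful-change analyses use the MITT population, which cannot exceed the number randomized.

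Fourth, the plan never compares a standard error with the 0.40 cut-off; that comparison is made here only to show scale. This is correct, and it is one reason the point is minor.

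**Conclusion.** The stated range does not follow from the plan's own figures. From 0.12 at n = 56, the standard error at n = 100 is 0.090, or 0.085 to 0.094 after allowing for rounding of 0.12 and for the choice of degrees of freedom. The 0.05 end is wrong as written: it is about 44% below the derived value (0.05/0.0898 = 0.56) and not attainable at r near 0.50 with 100 subjects. The 0.08 end is about 11% too low (0.08/0.0898 = 0.89), and at the edge of rounding if it is read as anything up to 0.085.

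This assumes the same correlation and estimator in both studies and that all 56 subjects contributed, since the text states no other change. The report behind the 0.12 was not available.

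Severity is minor. The convergent-validity criterion applies to the estimated correlation, no decision rule uses the standard error, and the 100 subjects rest on the primary-endpoint calculation and on feasibility.

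**What to change.** In SAP section 5.1 and in the Sample Size paragraph of the protocol synopsis, replace the range 0.05 to 0.08 with about 0.09, and show that it is 0.12 multiplied by the square root of 56/100. The cited 0.12 can stay.

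If the sponsor's range rests on another formula, on higher correlations or on fewer subjects behind the earlier estimates, state that basis next to the range. In particular, if the large-sample formula is intended, say so, give about 0.075 for r = 0.50, and note that the cited 0.12 does not come from that formula.

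The cost is one phrase in each document and a less favorable stated precision: a 95% half-width of about 0.18 on the first option. Enrollment, primary power and the planned analyses are unaffected.

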### 5.2 STATISTICAL AND ANALYTICAL PLANS

#### 5.2.1 Data management

All data will be collected on paper CRFs and diary cards.

All data from subjects who give written informed consent and for whom screening data are collected will be entered into a validated electronic database with a full audit trail of edits made. All data management will be performed in accordance with the current Standard Operating Procedures of the designated CRO. Adverse events and concomitant medications will be coded using the Medical Dictionary for Regulatory Activities (MedDRA) and the World Health Organization (WHO) drug dictionary respectively.

The database will be locked when there are no more data queries outstanding and all defined pre-database lock procedures are completed, including the identification of protocol deviations according to the pre-defined protocol deviation specifications.

The data will then be extracted into SAS® datasets for the purpose of statistical analysis and the generation of data presentations.

### 5.2.2 Response variables

Efficacy variables are defined in Section 4.1 and separated into primary, secondary and exploratory variables. It is of interest to estimate the effect of treatment on the success rate among study subjects and to test the null hypothesis that this effect is zero, versus that it is greater than zero. Also, subjects will be circumcised or uncircumcised, and it is of interest to evaluate the extent to which circumcision status might affect the overall success rate and whether the treatment effect is affected by circumcision status. For this pilot study subjects will be randomized to treatment based on site and circumcision status.

The psychometric variable is defined in Section 4.2.

Safety assessments will be based on study drug exposure, the nature, incidence, relationship and severity of AEs and SAEs, incidence of and reasons for withdrawals, laboratory parameters, use of concomitant medications, vital signs, findings on physical examination, 12-lead ECG and visual examination of the penis.

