Determine if the PSD502 group has a greater proportion of successful subjects on the PEBEQ Item 3 (event-specific bother) than does the placebo group, where success is defined for each subject as having a mean response over the 4-week treatment period at least 1 point better than the subject's mean response over the 4-week baseline period.

SECONDARY OBJECTIVES

Determine the psychometric properties of PEBEQ Item 3 (event-specific bother). In particular, the consistency in scoring of the PEBEQ Item 3 (event-specific bother) with the Patient Global Impression of Severity (PGI-S), Patient Global Impression of Change (PGI-C), Patient Global Impression of Change-Bother (PGI-C-Bother), Independent Ejaculation Quickness Item (IEQI) and Independent Numeric Response Scale (NRS) Bother Item and its responsiveness to change and derivation of meaningful change (anchor-based and other methods) will be evaluated. Other psychometric properties including reliability (test-retest reproducibility) and validity will also be evaluated.

Determine if the PSD502 group has a greater median score in the PGI-C and the PGI-C-Bother than does the placebo group.

Determine if the PSD502 group has a greater mean increase in the intravaginal ejaculatory latency time (IELT), the PGI-S, the Index of Premature Ejaculation® (IPE) Domain Scores, the Independent NRS Bother Item, and the IEQI than does the placebo group over the course of the study.

Evaluate safety and tolerability of PSD502 in subjects with PE and in their sexual partners.

EXPLORATORY OBJECTIVES

Determine if each of the PEBEQ multi-item scores are improved more in the PSD502 group than in the placebo group.

Other analyses suggested by the data.

Methodology:

This is a pilot, multicenter, randomized, double-blind, placebo-controlled clinical trial to evaluate the efficacy of PSD502 applied to the glans penis on bother-related symptoms secondary to PE. Additionally, psychometric evaluation of PEBEQ Item 3 (event-specific bother) will be investigated.

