#### Primary objective

The primary response variable is success on the PEBEQ Item 3 (event-specific bother), where success is defined *a priori* as having a 1-point or greater improvement between the mean response over the treatment period and the mean response during the baseline period. Success will be modelled using a generalized linear mixed effects model with treatment, circumcision status and baseline mean PEBEQ Item 3 (event-specific bother) score as fixed effects and site as a random effect. The model assumes a binomial family with logit link. The null hypothesis of no treatment effect will be tested after adjustment for these other covariates in the usual manner. From this model, estimated odds ratio of PSD502 to placebo and the corresponding 95% confidence interval will be calculated. The distributional assumptions of the model will be evaluated to ensure a satisfactory fit prior to statistical estimation and testing.

Additionally, the treatment effect for each circumcision status will be evaluated by adding the treatment-by-circumcision status interaction to the above model. From this model, estimated odds ratio of PSD502 to placebo and the corresponding 95% confidence interval for each circumcision status will be calculated.

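### Does the directional primary alternative leave the 5% significance level open to a one-sided test?

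*SAP*

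**What the plan says.** SAP Section 5.2.2 (Response variables) describes the interest in the treatment effect on the success rate and says the trial will "test the null hypothesis that this effect is zero, versus that it is greater than zero". The primary objective in the protocol synopsis is also directional: "Determine if the PSD502 group has a greater proportion of successful subjects on the PEBEQ Item 3 (event-specific bother) than does the placebo group".

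The significance level appears only in the sample-size text. SAP Section 5.1 claims adequacy "with power 80% using a chi square test with a 5% Type I error rate", and the protocol synopsis (Statistical Methods, Sample Size) repeats it. The scenario is 20% success on placebo, a difference of 30 points, 50 per arm and 10% dropout.

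The analysis itself is set out in SAP Section 5.2.3.8, Primary objective, as a mixed logistic model. There, "The null hypothesis of no treatment effect will be tested after adjustment for these other covariates in the usual manner", and the "estimated odds ratio of PSD502 to placebo and the corresponding 95% confidence interval will be calculated". No available text uses the term one-sided or two-sided.

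SAP Sections 5.2.3 and 5.2.3.12 say that a separate statistical analysis plan will be finalized before database lock. Section 5.2.3.5 plans no interim analysis.

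**The concern.** The only sentence that states the alternative is one-sided, and the only error rate is 5%. Put together literally, they describe a one-sided 5% test of the primary endpoint, with critical value 1.645 instead of 1.96.

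That would matter in three ways. The chance of wrongly declaring PSD502 better would be about twice that of a two-sided 5% test. A trial could be called positive while its own 95% interval for the odds ratio included 1. And if the choice were left open until the data were known, it could be made to suit them. The sample size also appears to have been computed for a different test from the one the literal reading gives.

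**Working it through.** **Inputs.** Success rates 20% and 50%, power 80%, Type I error 5%, chi-square test, dropout 10%, 50 per arm (SAP Section 5.1; protocol synopsis, Sample Size). The continuity correction tried below is not named in the documents.

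**Step 1: the plan's sample size.** The pooled formula is n = [z_α √(2p̄q̄) + z_β √(p₁q₁ + p₂q₂)]² / d², with p̄ = 0.35 and d = 0.30. Then √(2 × 0.35 × 0.65) = 0.6745, √(0.16 + 0.25) = 0.6403 and z_β = 0.8416.

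- Two-sided 5% (the same as one-sided 2.5%): (1.960 × 0.6745 + 0.8416 × 0.6403)² / 0.09 = 38.5.
- One-sided 5%: (1.645 × 0.6745 + 0.8416 × 0.6403)² / 0.09 = 30.2.

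The continuity correction multiplies n by ¼[1 + √(1 + 4/(nd))]², which gives 44.9 and 36.6. Dividing the rounded-up figure by 0.9 for dropout:

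| Reading | Uncorrected: evaluable → randomized | Corrected: evaluable → randomized |
|---|---|---|
| Two-sided 5% | 39 → 44 | 45 → **50** |
| One-sided 5% | 31 → 35 | 37 → 42 |

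Only two-sided 5% with the correction returns the plan's 50 per arm.

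**Step 2: what a 5% chi-square test is.** The statistic for a 2×2 table squares the difference, so it rejects in either direction. Its 5% critical value is 3.84 = 1.96². A one-sided 5% version needs the signed square root compared with 1.645, and neither document mentions this. A conventional 95% interval excludes the null value exactly when the matching two-sided 5% test rejects.

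**Step 3: how much the readings differ.** Exact binomial enumeration, 45 evaluable per arm. The first three data columns are the probability of rejecting in favor of PSD502 at critical value 1.645 / 1.96. The last counts rejections in both directions.

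| Test | 20% vs 20% | 20% vs 40% | 20% vs 50% | Total error of two-sided 5%, 20% vs 20% |
|---|---|---|---|---|
| Chi-square, uncorrected | 5.35% / 2.71% | 68.0% / 56.3% | 92.3% / 86.8% | 5.42% |
| Chi-square, corrected | 2.80% / 1.25% | 58.2% / 46.0% | 88.2% / 80.7% | 2.49% |
| Logistic Wald, unadjusted | 4.70% / 2.22% | 66.4% / 54.7% | 92.0% / 85.9% | 4.45% |

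For these three tests the readings reach different conclusions in about 5.5% to 7.5% of trials at the planned effect, and in about 12% at 20% against 40%.

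The planned mixed model was also simulated, with 10,000 trials per scenario. The assumptions are not in the documents: 70% circumcised with log odds ratio 0.3, log odds ratio 0.5 per baseline point, 30 sites, site SD 0 or 0.5 on the logit scale. The results are similar: 4.7–4.8% against 2.0–2.1% under no effect, and about 92% against 85% at the planned effect.

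**Step 4: a disputed result.** Take 9/45 on placebo and 17/45 on PSD502. The odds ratio is (17 × 36)/(28 × 9) = 2.43. The standard error of its log is √(1/17 + 1/28 + 1/9 + 1/36) = 0.483, so z = 0.887/0.483 = 1.84 and the 95% interval is 0.94 to 6.26. The one-sided p is 0.033 and the two-sided p is 0.066. With 9/45 on placebo and the unadjusted Wald test, this is the only PSD502 count in dispute: 16/45 misses both thresholds (z = 1.63) and 18/45 passes both (z = 2.04).

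**The case for a change.** The best case for a change is that the primary threshold should have one meaning, that the only explicit alternative is one-sided, and that adding the missing word would cost nothing. Calling the study a pilot is not an answer, since it has a powered primary hypothesis with a stated error rate. The sample-size match is also not proof: the text claims only that the number is sufficient, the match needs a correction the documents do not name, and the uncorrected two-sided formula gives 44.

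What stands is that the sides are not written down and that Section 5.2.2, taken alone, points the other way from the rest. What does not stand is the step from there to a planned one-sided 5% test. The sentence sits in a section on response variables, is framed as a matter of interest and carries no significance level. Directional wording is the documents' general style: the secondary objectives on medians and mean increases use it too. It is also fully compatible with one-sided 2.5%, which has the same sample size and the same threshold in favor of PSD502 as two-sided 5%.

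The worry about choosing after seeing the data is limited as well. The trial is double-blind with no interim look, the separate SAP must be final before lock, and Section 5.2.3.12 requires later changes to be reported with their rationale and a discussion of bias.

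**Conclusion.** This is a small ambiguity of wording that an analyst would fill correctly. The named test, the 95% interval and the sample size all point to two-sided 5%; one directional sentence does not, and even that can be read as one-sided 2.5%. An analyst following Section 5.2.3.8 would by default report the two-sided test that matches the interval.

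No stated figure or rule gives a wrong result. Across the exact calculations, total Type I error at a 20% success rate is at most 5.42% under either reading. Power at 20% against 50% with 45 evaluable per arm is at least 80.7%. The number randomized, the model and the interval are the same either way. The doubling of false claims is real arithmetic, but it applies only if someone adopts a reading that most of the text does not support.

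The conclusion assumes that the separate SAP names the sides before lock, as analysis plans ordinarily do. That document, and some SAP text ahead of Section 5, were not available here and may already settle the point. An explicit success rule based on the interval would be optional.
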